## **2.7 Safety analyses**

### **2.7.1 Adverse event during observational period**

Adverse event and serious adverse event during observational period will be summarized by primary system organ class and preferred term for OFAS.

### **2.7.2 Laboratory data**

Abnormalities in urinalysis result will be listed.

### 2.7.3 Liver events

To evaluate potential drug-induced liver injury, newly occurring liver enzyme abnormalities will also be summarized based on the event criteria given below. For potential Hy's Law case, all the elevations must occur at the same post-baseline timepoint. A case will be considered as newly occurring if a criterion is not met or missing at baseline but is met thereafter.

**Table 2-4 Liver enzyme abnormalities**

Parameter	Criterion
ALT	>3xULN; >5xULN; >8xULN; >10xULN, >20xULN
AST	>3xULN; >5xULN; >8xULN; >10xULN, >20xULN
ALT or AST	>3xULN; >5xULN; >8xULN; >10xULN; >20xULN
(ALT or AST) & TBL	>3xULN & (TBL>1.5xULN; >2xULN)
(ALT or AST) & INR	>3xULN & INR>1.5
TBL	>1xULN; >1.5xULN; >2xULN;
ALP	>1.5xULN; >2xULN; >5xULN
ALP & TBL	>3xULN; >5xULN & TBL>2xULN
(ALT or AST) & TBL & ALP	ALT or AST>3xULN & TBL >2xULN & ALP <2xULN ( Potential Hy's Law )

[REDACTED]

[REDACTED]

[REDACTED]

[REDACTED]

[REDACTED]

A series of 15 horizontal black bars of varying lengths, starting with short bars and increasing to long bars, with a small black square preceding the first bar.

### 3 Sample size calculation

It is expected that approximately 250 subjects from CLOU064A2201 study will enroll in this extension study. Additional subjects may roll over from other not-yet specified studies. █

## 4 Change to protocol specified analyses

Not applicable.

## 5 Appendix

### 5.1 Imputation rules

#### 5.1.1 Study drug

Partial dose date is not allowed in data collection.

#### 5.1.2 AE date imputation

##### Impute AE end date:

1. If the AE end date 'month' is missing, the imputed end date should be set to the earliest of the (last visit date, 31DECYYYY, date of death).
2. If the AE end date 'day' is missing, the imputed end date should be set to the earliest of the (last visit date, last day of the month, date of death).
3. If AE 'year' is missing or AE is ongoing, the end date will not be imputed.

##### Impute AE start date:

Before imputing AE start date, find the AE start reference date as below

- If the (imputed) AE end date is complete and the (imputed) AE end date < treatment start date then AE start reference date = min(informed consent date, earliest visit date).
- Else AE start reference date = treatment start date

1. If the AE start date 'year' value is missing, the date uncertainty is too high to impute a rational date. Therefore, if the AE year value is missing, the imputed AE start date is set to NULL.
2. If the AE start date 'year' value is less than the treatment start date year value, the AE started before treatment. Therefore:

- a. If AE 'month' is missing, the imputed AE start date is set to the mid-year point (01JulYYYY).
- b. Else if AE 'month' is not missing, the imputed AE start date is set to the mid-month point (15MONYYYY).

3. If the AE start date year value is greater than the treatment start date year value, the AE started after treatment. Therefore:

- a. If the AE month is missing, the imputed AE start date is set to the year start point (01JanYYYY).
- b. Else if the AE month is not missing, the imputed AE start date is set to the later of (month start point (01MONYYYY), AE start reference date + 1 day).

4. If the AE start date year value is equal to the treatment start date year value:

- a. And the AE month is missing the imputed AE start date is set to the AE reference start date + 1 day.
- b. Else if the AE month is less than the treatment start month, the imputed AE start date is set to the mid-month point (15MONYYYY).
- c. Else if the AE month is equal to the treatment start date month or greater than the treatment start date month, the imputed AE start date is set to the later of (month start point (01MONYYYY), AE start reference date + 1 day).

If complete (imputed) AE end date is available and the imputed AE start date is greater than the (imputed) AE end date, then imputed AE start date should be set to the (imputed) AE end date.

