# **10 Safety monitoring and reporting**

## **10.1 Definition of adverse events and reporting requirements**

### **10.1.1 Adverse events**

An adverse event (AE) is any untoward medical occurrence (e.g., any unfavorable and unintended sign [including abnormal laboratory findings], symptom or disease) in a subject or clinical investigation subject after providing written informed consent for participation in the study. Therefore, an AE may or may not be temporally or causally associated with the use of a medicinal (investigational) product.

The investigator has the responsibility for managing the safety of individual subject and identifying adverse events.

Novartis qualified medical personnel will be readily available to advise on trial related medical questions or problems.

The occurrence of adverse events must be sought by non-directive questioning of the subject at each visit during the study. Adverse events also may be detected when they are volunteered by the subject during or between visits or through physical examination findings, laboratory test findings, or other assessments.

Adverse events must be recorded in the Adverse Events CRF under the signs, symptoms or diagnosis associated with them, accompanied by the following information (as far as possible) (if the event is serious refer to [Section 10.1.2](#)):

1. The severity grade
  - mild: usually transient in nature and generally not interfering with normal activities
  - moderate: sufficiently discomforting to interfere with normal activities
  - severe: prevents normal activities

2. its relationship to the study treatment. If the event is due to lack of efficacy or progression of underlying illness (i.e. progression of the study indication) the assessment of causality will usually be 'Not suspected'. The rationale for this guidance is that the symptoms of a lack of efficacy or progression of underlying illness are not caused by the trial drug, they happen in spite of its administration and/or both lack of efficacy and progression of underlying disease can only be evaluated meaningfully by an analysis of cohorts, not on a single subject
3. its duration (start and end dates) or if the event is ongoing, an outcome of not recovered/not resolved must be reported.
4. whether it constitutes a SAE (see [Section 10.1.2](#) for definition of SAE) and which seriousness criteria have been met
5. action taken regarding with study treatment.

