#### **2.1.1.5 On-treatment**

All safety events happened after first dose of study treatment and before minimum(last dose + 28days, end of study visit) will be considered on-treatment no matter during treatment period or follow-up period.

For AE summary for observational period, all adverse event happened after enrollment in observational period and before roll over to treatment period will be summarized.

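### AE start-date rules 2a, 2b and 4b (SAP 5.1.2) have no floor at observational enrollment, so in two situations they date an observational-period event before enrollment

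*SAP*

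**What the plan says.** SAP 5.1.2 chooses a start-date rule by comparing the known part of the date with the treatment start date.

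- Rule 2a, start year before the treatment year, month unknown: "If AE 'month' is missing, the imputed AE start date is set to the mid-year point (01JulYYYY".
- Rule 2b, start year before the treatment year, month known: "Else if AE 'month' is not missing, the imputed AE start date is set to the mid-month point (15MONYYYY".
- Rule 4b, same year, earlier month: "Else if the AE month is less than the treatment start month, the imputed AE start date is set to the mid-month point (15MONYYYY".

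The section also defines a reference date. For an event that ended before treatment it is "AE start reference date = min(informed consent date, earliest visit date"; for any other event it is the treatment start date. Rules 3b and 4c use it as a lower bound ("set to the later of (month start point (01MONYYYY), AE start reference date + 1 day"), and rule 4a uses it directly ("the imputed AE start date is set to the AE reference start date + 1 day"). Rules 2a, 2b and 4b do not use it. The closing adjustment pulls a start back to the end date when the start falls after it. It can only move a date earlier, so it is not a floor.

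SAP 2.1.1.5 defines the observational AE summary: "all adverse event happened after enrollment in observational period and before roll over to treatment period will be summarized". SAP 2.7.1 reports it for oFAS by system organ class and preferred term. Protocol 10.1.1 defines an adverse event as an occurrence "in a subject or clinical investigation subject after providing written informed consent for participation in the study".

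**The concern.** Under Protocol 10.1.1 an adverse event starts after consent, and conditions already present at consent go to medical history. Consent is taken at enrollment (Protocol glossary), and Protocol Table 8-2 places it on Day 1 of the observational period. An imputed onset before enrollment therefore contradicts the definition under which the event was recorded.

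An event so dated also falls outside the SAP 2.1.1.5 window. The error has one direction: this mechanism can remove events from the observational AE and SAE table but cannot add any. What is at stake is the completeness of that table.

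**Working it through.** The plan states no figure on this point, so there is none to reproduce. The rules were applied literally to dates.

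**Inputs from the documents.** The three rules above; the window in SAP 2.1.1.5; an observational period of at most 12 weeks, or 84 days (Protocol section 3).

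**Assumptions, because the documents give no figures.** Enrollment on each of the 366 days of 2020; consent, earliest visit and enrollment on the same day; onset uniform over the days strictly between enrollment and treatment start; an observational period of L = 14, 28, 42, 56 or 84 days.

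**Day missing (rules 2b and 4b).** The 15th precedes enrollment only if the event month is the enrollment month and enrollment was after the 15th. The rules apply only if treatment starts in a later month. For enrollment on day d of a month with M days, M − d possible onset days remain in that month.

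- Misplaced, L ≥ 28: the sum of (M − d) over d = 16 to M is (M − 16)(M − 15)/2. That is 120 for a 31-day month, 105 for 30 days and 91 for 29 days. Total: 7 × 120 + 4 × 105 + 91 = 1,351.
- Enrollment-month events, L ≥ 42: M(M − 1)/2 per month. Total: 7 × 465 + 4 × 435 + 406 = 5,401.
- Enrollment-month events, L = 28: treatment falls in a later month only if d > M − 28, which gives 0 + 1 + … + 27 = 378 per month. Total: 12 × 378 = 4,536.
- L = 14: treatment falls in a later month only if d > M − 14, so d is at least 16 in every month. Each month gives 0 + 1 + … + 13 = 91. Total: 12 × 91 = 1,092, all misplaced.
- All observational events: 366 × (L − 1).

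| L (days) | All events | Enrollment-month events, treatment in a later month | Dated before enrollment | Share of all | Share of enrollment-month events |
|---|---|---|---|---|---|
| 14 | 4,758 | 1,092 | 1,092 | 23.0% | 100% |
| 28 | 9,882 | 4,536 | 1,351 | 13.7% | 29.8% |
| 42 | 15,006 | 5,401 | 1,351 | 9.0% | 25.0% |
| 56 | 20,130 | 5,401 | 1,351 | 6.7% | 25.0% |
| 84 | 30,378 | 5,401 | 1,351 | 4.4% | 25.0% |

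A further 0% to 1.9% land exactly on the enrollment day (enrollment on the 15th), where it is unclear whether they count as after enrollment.

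**Only the year known (rule 2a).** The rule applies when treatment starts in the calendar year after the event. With at most 84 days of observation, enrollment was then no earlier than 1 January minus 84 days, which is 9 October. The imputed 1 July always precedes that. Over all enrollment and treatment dates that cross a year end and lie 1 to 85 days apart (85 × 86/2 = 3,655 pairs), none puts 1 July on or after enrollment. The share of year-only events reaching rule 2a is [L(L − 1)/2] / [366(L − 1)] = L/732: 1.9% for 14 days, 11.5% for 84 days. The other year-only events go to rule 4a, which never gives a date before enrollment.

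**Examples.**

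- Enrollment 20 March 2020, treatment 15 May 2020, event start March 2020 with day unknown, end 2 April. Rule 4b gives 15 March, five days before enrollment.
- Enrollment 20 November 2020, treatment 15 January 2021, event start 2020 only, end 12 December. Rule 2a gives 1 July 2020.

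**The case against.** The effect is narrow. Between 77% and 96% of day-missing observational events are not dated before enrollment in these scenarios. SAP 2.1.1.5 does not say that its window uses the imputed start date, so loss from the table is inferred. Partial dates should be uncommon: missing values are queried to sites (Protocol 11.2), events are sought at each observational visit (Table 8-2), and serious events are reported within 24 hours of awareness (Protocol 10.1.3). All events are listed for all enrolled subjects (Protocol 12.5.2), so an omitted one stays visible. The table is descriptive.

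All of this stands, and it limits the size of the problem. It does not remove it: followed literally, the rules still give a date that the protocol's own definition excludes, and the SAP offers no date other than the imputed start on which to apply the window.

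Two stronger readings are tempting and are not supported.

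- A reader might infer that about half of day-missing enrollment-month events are lost, because 186 of the 366 dates in 2020 (50.8%) fall after the 15th. That counts enrollment dates, not events. Subjects enrolled late in a month have fewer days left in it, so the share is about 25% to 30% for periods of four weeks or more. In the 14-day scenario it is 100%, because only late-month enrollees then start treatment in a later month.
- A reader might infer that the primary safety analysis is distorted. Rules 2a, 2b and 4b act on events with a known year or month before treatment start and keep their onset before treatment, so new-onset treatment-emergent counts do not change through this defect.

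**Conclusion.** The point holds in a limited form. Rules 2a, 2b and 4b date an observational-period event before enrollment in two situations: (i) day missing, event in the enrollment month, enrollment after the 15th, treatment in a later month; (ii) only the year known and treatment in the next calendar year, where the event is always misplaced. Situation (i) covers 4.4% to 23.0% of day-missing observational events, with the highest share for the shortest period. These shares rest on uniform onset, enrollment spread evenly over the year, and consent on the day of enrollment. Loss from the oFAS table further assumes that the window uses the imputed start date. The absolute number of events cannot be computed, because the share of partly dated events is not given; it is probably small. This is a low-priority correction to one descriptive table.

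**What to change.** In rules 2a, 2b and 4b, for oFAS subjects, set the imputed start to the later of the present value and observational enrollment date + 1 day, capped at the AE end date. With this floor no event falls before enrollment in any scenario above, and the two examples become 21 March 2020 and 21 November 2020, both inside the window.

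Name the enrollment date, not the AE start reference date. The reference date becomes treatment start for events that are ongoing or that end on or after treatment start, so it is an enrollment-type floor only for events that ended earlier.

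Add a rule for oFAS subjects who never relapse and are never treated. Rules 2 to 4 all compare with a treatment start date that these subjects do not have. Apply the same enrollment floor to the start of the known month or year.

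The cost is a short edit to SAP 5.1.2 and the matching lines in the derivation program. No new data are needed.

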### **5.1.3 Concomitant medication date imputation**

#### **Impute concomitant medication (CM) end date:**

1. If CM end day is missing and CM month/year are non-missing then impute CM day as the minimum of treatment end date and the last day of the month.
2. If CM end day/month are missing and CM year is non-missing then impute CM day as the minimum of treatment end date and the end of the year (31DECYYYY).
3. If imputed CM end date is less than the CM start date, use the CM start date as the imputed CM end date.

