#### **2.4.2 Prior, concomitant and post therapies**

Prior, non-urticaria related concomitant medications and urticaria related concomitant medication or rescue medications during treatment period will be summarized by Anatomical Therapeutic Chemical (ATC) code and preferred term for SAF. Additionally, concomitant surgeries, medical procedures and non-drug therapies by primary system organ class and preferred term will be preseted.

Concomitant medications are defined as any medication given at least once between the day of first dose of study treatment and the date of the last study visit.

Background medications and rescue medications during treatment period will be summarized separately by Anatomical Therapeutic Chemical (ATC) code and preferred term for SAF.

Medications will be identified using the Novartis Drug and Therapy Dictionary (NovDTD) including the Anatomical Therapeutic Chemical (ATC) code. Medications will be presented in alphabetical order, by ATC code.

All relevant listings will be provided based on SAF for concomitant medication; concomitant surgeries, medical procedures and non-drug therapies.

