#### **Impute CM start date:**

1. If the CM start date year value is missing, the imputed CM start date is set to one day prior to treatment start date.
2. If the CM start date year value is less than the treatment start date year value, the CM started before treatment. Therefore:
  - a. If the CM month is missing, the imputed CM start date is set to the mid-year point (01JulYYYY).
  - b. Else if the CM month is not missing, the imputed CM start date is set to the mid-month point (15MONYYYY).
3. If the CM start date year value is greater than the treatment start date year value, the CM started after treatment. Therefore:
  - a. If the CM month is missing, the imputed CM start date is set to the year start point (01JanYYYY).
  - b. Else if the CM month is not missing, the imputed CM start date is set to the month start point (01MONYYYY).
4. If the CM start date year value is equal to the treatment start date year value:
  - a. And the CM month is missing or the CM month is equal to the treatment start date month, then the imputed CM start date is set to one day prior treatment start date.
  - b. Else if the CM month is less than the treatment start date month, the imputed CM start date is set to the mid-month point (15MONYYYY).
  - c. Else if the CM month is greater than the treatment start date month, the imputed CM start date is set to the month start point (01MONYYYY).

If complete (imputed) CM end date is available and the imputed CM start date is greater than the (imputed) CM end date, then imputed CM start date should be set to the (imputed) CM end date.

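### SAP 5.1.3 caps a partial medication end date at treatment end even when the recorded month is later, so a completer's follow-up-only drug can enter the treatment-period medication tables

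*SAP*

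**What the plan says.** SAP 5.1.3 has two rules for a partial medication end date. With the day missing, it is to "impute CM day as the minimum of treatment end date and the last day of the month". With day and month missing, it is to "impute CM day as the minimum of treatment end date and the end of the year (31DECYYYY"). A third rule is a safeguard: "If imputed CM end date is less than the CM start date, use the CM start date as the imputed CM end date".

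The start-date rules follow. For a day-missing start in a year after the treatment-start year: "Else if the CM month is not missing, the imputed CM start date is set to the month start point (01MONYYYY"). The section closes with an override for an imputed start that falls after the end: "then imputed CM start date should be set to the (imputed) CM end date".

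The dates feed SAP 2.4.2. Concomitant medication there is "any medication given at least once between the day of first dose of study treatment and the date of the last study visit", which includes follow-up. The same section adds a narrower display: "Background medications and rescue medications during treatment period will be summarized separately". SAP 1.1 ends the treatment period at Week 52, with follow-up visits added only for patients who discontinued prematurely.

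The neighbouring rule for adverse event end dates (SAP 5.1.2) uses a different cap when the day is missing: "the earliest of the (last visit date, last day of the month, date of death").

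**The concern.** A cap at treatment end is harmless when the recorded month is the month of treatment end or earlier. When the recorded month is later, the rule gives an end date that the site's own entry rules out. The closing start-date rule then treats that date as reliable and can pull the start back to it, so a drug known to have begun after treatment is dated to the last treatment day.

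Drug use in follow-up is foreseeable. Protocol Section 3 allows rescue H1-antihistamine throughout the study, and follow-up lasts 4 to 16 weeks. For a completer, the misdated record can appear in the background or rescue table for the treatment period and overstate use while on LOU064. Where the start is not moved, the record of use in follow-up can still be cut short.

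**Working it through.** The plan states no figure to reproduce, so the check applies the rules of SAP 5.1.3 as written to an assumed subject.

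**Assumed inputs**
- First dose 15 June 2020.
- Treatment end 13 June 2021, which is 363 days later, the last day of 52 weeks. SAP 5.1.3 does not define treatment end date; last dose is assumed.
- Last visit 3 October 2021, which is 13 June plus 112 days (16 weeks). This is a completer in extended follow-up.

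**Formulas**
- Imputed end = min(treatment end, last day of recorded month), or min(treatment end, 31 December of the recorded year).
- If imputed end < start, then end = start (rule 3).
- Start with day missing, in a year after the treatment-start year = first of the recorded month.
- If imputed start > end, then start = end (closing rule).

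**Case (a), end date first.** Recorded start and end are both August 2021, days unknown.
1. End = min(13 June, 31 August) = 13 June 2021.
2. Rule 3 cannot act, because the start is still partial.
3. Start = 1 August 2021, which is later than 13 June, so start = 13 June 2021.
4. Shift of the start = 17 + 31 + 1 = 49 days, or 7 weeks.

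All cases (dates in 2021; ? = part not recorded). The last column gives the same result in either order.

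| Case | Recorded start | Recorded end | As written, end first | As written, start first | Cap at last visit |
|---|---|---|---|---|---|
| a | ? Aug | ? Aug | 13 Jun to 13 Jun | 1 Aug to 1 Aug | 1 Aug to 31 Aug |
| b | ? Aug | ? ? (year only) | 13 Jun to 13 Jun | 1 Aug to 1 Aug | 1 Aug to 3 Oct |
| c | 10 Aug | ? Aug | 10 Aug to 10 Aug | same | 10 Aug to 31 Aug |
| d | ? Aug | 20 Aug | 1 Aug to 20 Aug | same | same |
| e | 10 May | ? Aug | 10 May to 13 Jun | same | 10 May to 31 Aug |
| f | ? Jun | ? Aug | 1 Jun to 13 Jun | same | 1 Jun to 31 Aug |
| g | ? ? (year only) | ? Aug | 1 Jan to 13 Jun | same | 1 Jan to 31 Aug |

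**Reading the table**
- Only (a) and (b) move from follow-up into treatment, and only when the end is imputed first.
- In (c), rule 3 keeps the drug in follow-up but cuts it to one day.
- In (d), the complete end date means that the cap is never applied.
- In (e), the drug was already in use on treatment; only its follow-up part is lost.
- In (f) and (g), the start rule itself places the drug on treatment, whichever cap is used.

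**Order of imputation.** The SAP does not state it. The end rules come first, and the closing start rule refers to an end date that may already be imputed, whereas rule 3 refers simply to the start date. End first is therefore the natural reading.

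**The case against.** The strongest reply is that the effect is narrow and the tables are descriptive. Most of that stands.

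- **Conditions.** Both dates must be partial, the recorded start month must be after the month of treatment end, and the end must be imputed first. Reversing the order removes the shift.
- **Who is exposed.** Premature discontinuers are not reclassified, because SAP 1.1 already counts their follow-up visits in the treatment period. Among completers, follow-up beyond 4 weeks is only for those with UAS7 of 6 or less at Week 52, and it stops at relapse.
- **Size in the tables.** If the tables count subjects (an assumption), a moved record matters only when that subject never took the same preferred term during treatment. Protocol 6.2.3 has the rescue drug chosen once per subject, so a repeat of the same term is plausible.

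Two stronger readings are tempting but unsupported. A reader might infer that the misdating obscures whether UAS7 results were obtained on monotherapy. Monotherapy is required only from Day 1 to Week 4, a displaced record lands at about Week 52, and the UAS7 rules shown in SAP 2.6.3 use no medication date. A reader might also infer that every medication with partial dates in follow-up is displaced; (f) and (g) show that a partial start can already fall on treatment without the cap.

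What the reply does not answer is that a stated rule yields dates that contradict recorded data. The reverse order does not cure this: in (a) it still cuts a drug with an unknown end day in August to 1 August alone. Two programmers could follow the SAP and produce different tables.

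**Conclusion.** The point holds in this limited form. The cap at treatment end is wrong whenever the recorded end month or year extends beyond it and the drug was in fact still in use. Under the natural processing order, it can move a completer's follow-up-only medication onto the last treatment day and so into the background or rescue tables.

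Where the shift occurs, it is always towards the treatment period. Its length is the time from treatment end to the first of the recorded start month: 49 days in the example, and within the planned 4 to 16 weeks of follow-up. The documents give no count of partial dates, so the effect on any table percentage cannot be estimated.

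Concomitant status is unaffected because it runs to the last study visit. The primary safety analysis and all UAS7 analyses, including Week 4, are also unaffected. The verdict rests on treatment end meaning last dose or end of treatment, and on end dates being imputed first. It is a small defect, worth correcting because the repair is nearly free.

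**What to change.** 1. In SAP 5.1.3 end-date rules 1 and 2, replace treatment end date with the earlier of last study visit date and date of death, keeping the month-end or year-end limit. This matches the adverse event rule in SAP 5.1.2 and the reach of the concomitant definition in SAP 2.4.2.
2. State that the end date is imputed before the start date.

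In the cases above, the new cap keeps (a) and (b) in follow-up in either order and restores the lost follow-up use in (c) and (e).

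A general ban on an imputed date leaving its recorded month or year should not be added. It would conflict with the last-visit cap when the recorded month is after the last visit. It would also conflict with start rule 4a, which sets the day before treatment start, when treatment starts on the first of a month.

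The cost is a short wording change, one sentence on order, a small program edit and a rerun of the medication tables and listings. No new data are needed.
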